9. QUALITY ASSURANCE AND QUALITY CONTROL

Quality Assurance pertains to activities that promote collection of high-quality data, and Quality Control refers to activities that detect emerging data issues with sufficient time to implement appropriate corrective actions. Our approach to Quality Assurance includes: 1) preparing a manual of operations; 2) implementing a master trainer model to train and certify other staff; 3) train and certify all data collectors on in-person and remote procedures; 4) recertify data collectors at least annually; 5) routinely calibrate equipment; 6) maintain logs of certified staff and calibrated equipment. Our approach to Quality Control includes: 1) monitoring counts of completed data collection items; 2) monitoring distribution of trial outcomes, overall, by data collector and site; 3) record lag time in data entry; 4) issue queries on missing data, out of range values or illogical data relations; 4) review types and distribution of data entry errors; and 5) prepare reports for staff, investigators, and an independent study monitor on Quality Control.

10. RANDOMIZATION AND BLINDING

Following baseline data collection, sites will be randomized to the standard or enhanced arms. Randomized blocks of 2 in random order will be used to create the randomization sequence. The random sequence and allocation groupings will be stored in RedCap, only the data analyst will distinguish the treatment assignment to sites. Due to the nature of the intervention, both participants and interventionists will be aware of the assignment. Data collectors measure study outcomes. Investigators, staff and participants are masked to outcome data, with the exception of trial statistician, study coordinator, data analyst and independent study monitor.

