4. DESIGN SUMMARY

The core design is a randomized, two-arm, parallel, pilot clinical trial where 10 psychiatric rehabilitation program sites will be randomized to a 6-month standard or enhanced intervention. This trial will recruit and enroll participants at each site – staff, peer leaders, and mental health consumers, (Figure 1). The primary outcome variables will be coaches' knowledge, self-efficacy, and fidelity to the ACHIEVE curriculum.

Figure 1. Study Populations with Corresponding Activities and Outcomes for Each Site

We estimate up to 280 mental health organization staff and peer leaders will participate in data collection including program directors, coaches, and other psychiatric rehabilitation program staff. Two coaches and one peer leader per study site will be randomized to the standard or enhanced intervention. Up to 120 mental health consumers across all sites will be enrolled, and all will receive group weight-management sessions delivered by the trained coaches at their site.

The ACHIEVE-D curriculum is designed to fit into and will be part of the regular psychiatric rehabilitation programming that is already being conducted.

Randomized groups:

Standard intervention: At those sites assigned to the standard group, two staff and one peer will receive training and approximately 8-12 consumers with SMI will participate in the ACHIEVE weight loss program. The standard intervention will combine onboarding training, ongoing online training, and online avatar-assisted motivational interviewing practice^{19,20} for all coaches, as well as organizational strategy meetings to garner the leadership support for ACHIEVE implementation²¹.

Enhanced intervention: At those sites assigned to the enhanced group, the implementation intervention will include all standard strategies and will add performance coaching for the coaches.

Trainings and meetings will be remote during the COVID-19 pandemic.

We outline the eligibility criteria sites in Section 5. Then, we describe the eligibility criteria as well as data collection and measurements for each study population separately in Sections 6-8.

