11.1 ACHIEVE Curriculum

All sites will use the ACHIEVE curriculum, a six-month behavioral weight loss program delivered by trained coaches with the assistance of peer leaders to enrolled mental health consumers at the 10 PRPs. ACHIEVE classes will be offered at least once per week (up to 3 days per week) for about 1 hour. Classes may be

delivered in person or virtual depending on COVID restrictions in place at each PRP. Obesity is a chronic condition which benefits from ongoing intervention, and the curriculum is designed to be integrated into regular PRP programming. The curriculum includes six monthly core modules and seasonal modules that can be incorporated into the curriculum depending on the time of year the program is delivered (Exhibit 1). Within each monthly module, the topic varies by week. When sites are delivering more than one weight management class each week, the content will be repeated ; repetition of messages is a key tenet of intervention tailoring for persons with SMI. Coaches will use motivational interviewing communication techniques in all interactions with consumers. This curriculum was adapted from the behavioral intervention previously tested by [name] and colleagues¹⁵. We have also previously tested two months of this adapted curriculum at one PRP in a proof-of-concept study, which found that the format was feasible and acceptable to consumers and staff.

Exhibit 1. 6-Month ACHIEVE Curriculum Overview	
Type and Frequency of Contact	
Multipurpose group weight management class: 1-3 times per week for 50-min class (30 min weight management and 20 min exercise (see above)) led by trained ACHIEVE staff and peer coaches	
Weigh-ins: occur on the day of each class (10 min) (or virtually)	
Curriculum Delivery Modality	
Weight management: Facilitated session with short videos	
Exercise: Video-assisted group exercise	
Goals and Recommendations	
Weight loss goal 5% in 6 months	
Behavioral recommendations: 6 Core Modules Weight loss success	

 • No sugar drinks • No junk food • Eat smart portions • Eat more vegetables • Putting it all together 	
Seasonal modules available to tailor experience	

 • A New Start in the New Year • Heart Healthy Valentine's Day • Maintain Don't Gain during Celebrations • Spring into Walking • Halloween Fun without the Sugar • Maintain Don't Gain during the Holidays 	

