11.3 Enhanced Intervention Group

The enhanced intervention includes all components of the standard intervention along with the addition of performance coaching. Performance coaching may be particularly beneficial when, as in the present case, the evidence-based practice is new to most implementers. Each month a master trainer on the study team will meet with the Coach to provide tailored feedback and performance coaching session. The feedback will be used to 1) promote curriculum fidelity; 2) facilitate motivational interviewing skill development; and 3) help coaches plan for improved ACHIEVE curriculum delivery.

12. DATA MANAGEMENT and SECURITY

Quantitative Data. Each participant will be assigned a unique study ID number for data collection, instead of name or other identifying information. The link between identifying information and the study ID will be kept in a separate database with password access available only to the data analyst, statistician and principal investigators. Study team members are trained to protect integrity and confidentiality of the data. Data will be published only in aggregate, with no identifying characteristics of individuals published or presented. We will store data in a Johns Hopkins REDCap database. REDCap data is housed on secure servers at the Johns Hopkins Biostatistics Center under firewall protection. Database access is password protected and restricted to authorized personnel only and REDCap provides audit trails for tracking data manipulation and user activity. Any paper records will be kept in locked file cabinets. Kognito, a health simulation company, developed the avatar simulations for this project and hosts the avatar training platform and dashboard. Avatar performance measurement data for motivational interviewing practice conversations is accessible only by the individual study participant (provider) and the study team, not shared outside Kognito. Kognito stores data securely behind two firewalls.

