13. DATA ANALYSIS

We will assess the effects of the implementation intervention on providers' knowledge self-efficacy, and fidelity to the ACHIEVE curriculum, as well as consumer outcomes using generalized linear mixed-effects models under the intent-to-treat approach. Mean models will include a binary intervention group indicator, time indicators, intervention by time interaction terms, and fixed effects for the 10 study sites. The time indicator coefficients estimate time-specific mean outcome changes in the "standard" group and interaction coefficients estimate the between-arm differences of time-specific outcome changes from baseline. The linear combination of these time-specific coefficients captures the time-specific mean outcome changes in the "enhanced" group. The model will use an unstructured variance covariance matrix for the repeated outcome measurements over time within individuals. To assess whether knowledge and self-efficacy mediate implementation intervention

effects, we will estimate the magnitude of attenuation on intervention effects in the consumer outcome models with vs. without these measures. We will also examine potential moderators, e.g. study sites' implementation intervention fidelity and/or implementation climate, by adding appropriate interaction terms to the models. We will analyze survey data on our implementation measures prior to conducting focus groups in order to explore survey findings in depth (e.g., if providers' rate performance coaching as having mediocre acceptability, we will explore reasons why in the focus groups). We will use descriptive statistics to analyze survey measures of perceptions of acceptability, feasibility and appropriateness of implementation intervention and ACHIEVE-D. Point estimates and corresponding 95% confidence intervals will be obtained.

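### Section 10's reason for open assignment does not fit consumers, so the protocol should state arm awareness separately for each population and not disclose the arm to consumers before their 6-month self-reports

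*Combined protocol and SAP*

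**What the plan says.** Section 10 covers awareness of the arm in one sentence: "Due to the nature of the intervention, both participants and interventionists will be aware of the assignment". It does not distinguish the study populations. Section 4 does: "This trial will recruit and enroll participants at each site – staff, peer leaders, and mental health consumers".

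On what consumers receive, Section 4 says that "all will receive group weight-management sessions delivered by the trained coaches at their site", and Section 11.1 says: "All sites will use the ACHIEVE curriculum, a six-month behavioral weight loss program". On how the arms differ, Section 11.3 says: "The enhanced intervention includes all components of the standard intervention along with the addition of performance coaching". That section describes the addition as a monthly meeting between a master trainer and the coach.

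On timing, Section 10 says: "Following baseline data collection, sites will be randomized to the standard or enhanced arms". On analysis, Section 13 covers the coach outcomes "as well as consumer outcomes using generalized linear mixed-effects models under the intent-to-treat approach", with intervention-by-time terms that estimate between-arm differences in change.

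Section 10 also says that the data analyst alone can tell which site is in which arm. The masking it gives to investigators, staff and participants is to outcome data, not to arm.

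**The concern.** The stated justification is that the intervention cannot be hidden. That is true for a coach who does or does not receive performance coaching, and for the master trainer who gives it. It is not evidently true for a consumer, who attends the same kind of group in either arm and takes no part in the added component.

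At stake is part of Secondary Aim 2. Consumers who know that their site is in the arm labelled enhanced might describe their diet, activity or satisfaction more favourably, whatever the coach actually delivers. On self-report alone, such a shift would look like an effect of coaching. The same consumer outcome models feed the mediation analysis in Section 13. A reporting shift would not act through coach knowledge or self-efficacy, so it could also distort the reading of how much those measures attenuate the arm effect.

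**Working it through.** The protocol gives no figure on this point, so the check is mainly a comparison of sections.

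**1. Does the awareness sentence cover consumers?** Section 10 refers to participants without qualification, and Section 4 lists staff, peer leaders and consumers as participants. Read literally, consumers are included. A narrower reading is possible, because Section 4 also speaks of two coaches and one peer leader per site as the people randomized. The text does not settle which is meant.

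**2. Does the reason apply to consumers?** Sections 4 and 11.1 give every site the same curriculum. Section 11.3 adds one component, delivered to the coach. Nothing in the planned consumer-facing programme marks the arm.

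**3. Must consumers learn the arm at entry?** No. Sites are randomized after baseline, so the arm is unknown when consumers consent and give baseline data. Only follow-up reports can be affected.

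**4. Which outcomes are exposed?** Table 5 marks these self-report instruments at 6 months:
- Named in Secondary Aim 2: sedentary behaviour (1); Block fat, Block fruit/vegetable, eating away from home, sugar-sweetened beverages and the NHIS screener (5); satisfaction (1). Total 1 + 5 + 1 = 7.
- Listed under other measures: PEMS coping, RED, Important Others and PSS (4). These are not named in the aim.

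Satisfaction is collected only at 6 months, so it has no pre-randomization value to compare with. Attendance is a process record. Weight is read from a scale, although Sections 7.2 and 7.3 allow self-measurement when the visit is remote.

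**5. Is there another safeguard?** Not a clear one. The sentence restricting knowledge of the allocation to the data analyst cannot stand literally beside the sentence that participants and interventionists know it. Nothing states whether the 6-month data collectors know the arm.

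**6. Sensitivity, for illustration only.** The documents give no reporting shift, intraclass correlation (ICC) or significance level for consumer outcomes. Assume 5 sites per arm (10 sites, blocks of 2), m = 8 or 12 consumers per site (the range in Section 4, so n = 40 or 60 per arm), ICC 0.02 to 0.10, one 6-month score in SD units, and a two-sided 5% test.

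SE = √[(2/n) × (1 + (m − 1) × ICC)]
- m = 12, ICC 0.02: √(0.0333 × 1.22) = 0.20
- m = 8, ICC 0.10: √(0.05 × 1.70) = 0.29

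Error rate = P(|Z + shift/SE| > 1.96):

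| Assumed shift | Normal reference | t reference, 8 df |
|---|---|---|
| 0.1 SD | 6.4–7.9% | 6.1–7.2% |
| 0.2 SD | 10.5–16.8% | 9.3–14.2% |

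With 10 sites the t column is the more suitable one. The planned model uses change from baseline where a baseline exists, so neither column describes it exactly. The table shows what a given shift would do. It is not evidence that a shift of that size, or any shift, will occur.

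**The case against.** A reader might infer that the plan has consumers told which arm they are in, and that their reports are therefore biased. The documents do not support this. No section says that consumers will be told. The consent script is not available for this review, and Section 14 says only that the scripts cover the data-collection and intervention procedures. The script may already be neutral. This part of the objection stands: the finding concerns an unsuited justification and an unstated safeguard, not demonstrated unblinding.

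It is also tempting to say that consumers could be kept unaware at no cost. That is too strong. Coaches know the arm and lead the groups at least weekly. Peer leaders train alongside them, and Section 6.1 allows a peer leader to be a mental health consumer. Some leakage is likely. Incomplete concealment is still better than planned awareness, so this limits the benefit without removing the point.

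A third tempting reading is that study staff who know the arm will read the 6-month questionnaires to consumers. The description in Section 7.2 of staff reviewing or reading surveys belongs mainly to the visit at which consent is obtained, before randomization. It is weak evidence about the 6-month assessment.

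Finally, both arms receive an active programme, and consumers have little evident reason to answer differently because of a coach's monthly meeting. Weight, attendance and video-rated fidelity offer some corroboration. The hypotheses H1.1 and H1.2 concern knowledge, self-efficacy and fidelity of delivery; Aim 2 only sets out to assess consumer outcomes. These points stand and keep the matter minor. They do not make the Section 10 justification fit consumers.

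**Conclusion.** The point holds in a limited form, as a cheap improvement. The blanket reason for open assignment does not apply to consumers, and the protocol neither says whether they are told the arm nor secures that they are not. The exposure is confined to self-reported secondary outcomes compared by arm: seven instruments under Secondary Aim 2. The primary coach outcomes, knowledge, self-efficacy and fidelity, are untouched.

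No size can be put on the bias from the documents, and it may be small. The conclusion rests on two readings: that participants in Section 10 has the meaning given in Section 4, and that performance coaching is the only planned difference between arms, as Section 11.3 states. If the sponsor meant only coaches and peer leaders, the remedy is the same clarification.

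**What to change.** Revise Section 10 to state awareness of the arm separately for each population:
- Coaches, peer leaders, site leaders and master trainers know the assignment.
- Consumers are not told their site's arm until their 6-month self-reports are complete. Consent wording should be neutral about the arms, if it is not already.
- The existing data collectors who administer the 6-month consumer questionnaires are not given the arm.

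Reconcile this text with the sentence that restricts knowledge of the allocation to the data analyst.

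The cost is a short rewording, possible IRB review of the script, and an instruction on who receives the allocation. No added visits or consumers are needed. Masking will be incomplete, and the protocol should say so. If consumers have already been told their arm, or their 6-month data are already collected, record what they were told and report it as a limitation of the self-reported comparisons.

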11. INTERVENTION GROUPS

An overarching principle of the adapted ACHIEVE-D curriculum is that it is designed to fit into and will be part of the regular programming that psychiatric rehabilitation programs are already providing for their clients with mental illness. The psychiatric rehabilitation program staff trained as ACHIEVE-D coaches will have the support of their leadership for ACHIEVE-D program delivery. Based on discussions with and requests from the study sites, each site will decide how they will deliver the ACHIEVE-D curriculum during COVID, taking into consideration how they are delivering their other programming, their priorities, and resources. If psychiatric rehabilitation programs are delivering in-person programming, then they will likely plan to deliver ACHIEVE-D in-person at least once per week. For persons with serious mental illness, in-person programming is preferred due to psychiatric symptoms, cognitive impairment, and potential challenges using smartphones and computers. To support sites that prefer to offer remote groups, we will be providing clients with Grandpads (tablets). Our study team will train consumers to use the devices during baseline data collection and Coaches will troubleshoot technology issues that arise during groups. We expect most sites will use a hybrid method of delivery during COVID with both in-person and remote sessions. Sites follow Maryland Medicaid and other regulatory guidelines for safety and operating procedures. Sites will have the flexibility to change their delivery method during the study. (We have discussed these plans with [name]). Peer leaders will assist staff coaches as appropriate including considering COVID restrictions at each site.

In-person group exercise classes may be held during COVID-19 depending on each site's COVID safety protocol. Exercise classes may be delivered via Zoom video-conferencing as part of the ACHIEVE group or offered as a supplemental session led by a trained peer leader with support from the study team.

11.1 ACHIEVE Curriculum

All sites will use the ACHIEVE curriculum, a six-month behavioral weight loss program delivered by trained coaches with the assistance of peer leaders to enrolled mental health consumers at the 10 PRPs. ACHIEVE classes will be offered at least once per week (up to 3 days per week) for about 1 hour. Classes may be

delivered in person or virtual depending on COVID restrictions in place at each PRP. Obesity is a chronic condition which benefits from ongoing intervention, and the curriculum is designed to be integrated into regular PRP programming. The curriculum includes six monthly core modules and seasonal modules that can be incorporated into the curriculum depending on the time of year the program is delivered (Exhibit 1). Within each monthly module, the topic varies by week. When sites are delivering more than one weight management class each week, the content will be repeated ; repetition of messages is a key tenet of intervention tailoring for persons with SMI. Coaches will use motivational interviewing communication techniques in all interactions with consumers. This curriculum was adapted from the behavioral intervention previously tested by [name] and colleagues¹⁵. We have also previously tested two months of this adapted curriculum at one PRP in a proof-of-concept study, which found that the format was feasible and acceptable to consumers and staff.

Exhibit 1. 6-Month ACHIEVE Curriculum Overview	
Type and Frequency of Contact	
Multipurpose group weight management class: 1-3 times per week for 50-min class (30 min weight management and 20 min exercise (see above)) led by trained ACHIEVE staff and peer coaches	
Weigh-ins: occur on the day of each class (10 min) (or virtually)	
Curriculum Delivery Modality	
Weight management: Facilitated session with short videos	
Exercise: Video-assisted group exercise	
Goals and Recommendations	
Weight loss goal 5% in 6 months	
Behavioral recommendations: 6 Core Modules Weight loss success	

 • No sugar drinks • No junk food • Eat smart portions • Eat more vegetables • Putting it all together 	
Seasonal modules available to tailor experience	

 • A New Start in the New Year • Heart Healthy Valentine's Day • Maintain Don't Gain during Celebrations • Spring into Walking • Halloween Fun without the Sugar • Maintain Don't Gain during the Holidays 	

during COVID-19 with appropriate safety protocols (e.g., social distancing, proper room ventilation). Exercise classes may also be delivered via Zoom video-conferencing as part of remote groups. For remote sessions, exercise class will occur during the first 20 minutes of the session via Zoom. The coach may play an exercise video over Zoom. If the site is using a hybrid model of delivery with some weight management sessions

occurring in-person, the coach may offer additional physical activity classes to be delivered via Zoom or recommend online exercise videos for participant. The coach will recommend daily physical activity for at least 20 minutes, whether in an ACHIEVE session or not, specifically emphasizing low impact moderate intensity aerobic exercises such as going on walks.

Video-based virtual exercise classes may also be offered as a separate group that is facilitated by the peer leader and study team staff. The peer leader will be trained to co-lead these groups using an ACHIEVE-approved low-impact moderate intensity aerobic video (e.g., Walk Away the Pounds). Groups will last 20 minutes and include a warm-up and cool-down. To ensure participant safety, the study team member will confirm each participants' contact information at the beginning of each class (e.g., name, address from which they are joining the exercise class, phone number and emergency contact). The peer leader will facilitate the class, and the study team member will monitor participants via video. These groups will be scheduled at times that do not conflict with the Coach-led ACHIEVE groups. When sites are delivering in-person groups and are not able to incorporate group exercise into the curriculum (due to COVID safety protocols), these virtual exercise classes provide an option for clients to engage in exercise from the safety and convenience of their home while also benefiting from the support of their peers.

